**CONFIDENTIAL**

---

and root planing with or without adjunctive laser therapy and periodic periodontal recall maintenance over the course of 12 months while enrolled in the study. Any other non-periodontal dental treatment needs that may be deemed necessary will be the patient's responsibility.

**Human Subjects and Privacy.** This study proposal is being submitted to the UCLA Human Research Protection Program (HRPP) for IRB approval. A similar protocol using an Er:YAG laser has been approved. It is anticipated that this protocol will be approved.

**CONFIDENTIAL****ATTACHMENT 1****REPaIR Protocol (Regenerative, Er,Cr:YSGG, Periodontitis, ai, Regimen)**

- 1) Surgical preparation: Following patient identification, review of health history and checking vital signs, local anesthesia is applied to the area.
- 2) Outer pocket de-epithelialization: The outer pocket gingival epithelium is removed (and gingivectomy performed if pseudopocket) with laser. Setting: RFTP5, 1.5W, 15% air, 15% water, 30 Hz, H mode (iPlus preset).
- 3) De-epithelialization and retraction: The inner pocket epithelium is removed from the free gingival margin to the level equal with the pocket depth. Setting: MZ6, 1.5W, 11% air, 20% water, 30 Hz, H mode (iPlus preset).
- 4) Scaling and Root Planing: Conventional treatment with hand instruments and ultrasonics to remove root surface accretions /calculus, and to smooth root surface cementum/dentin.
- 5) Sulcular Debridement / Degranulation: The purpose of this step is to remove smear layer from root surface, to completely remove pocket lining and to degranulate the pocket. Setting: RFPT5, 1.5W, 20% air, 40% water, 30 Hz, H mode (iPlus preset).
- 6) Bone Decortication: The purpose of this step is to recontour osseous defects and to stimulate bone regeneration. The tip is held parallel to the root surface while gently tapping all the way down to bone at the base of the defect. The laser slightly penetrates the bone at each point as this step is repeated stepwise around the tooth. The angle of the tip maybe changed to treat the walls of the intrabony defect. Setting: MZ6, 2.5W, 70% air, 80% water, 30 Hz, H mode (iPlus preset).
- 7) Sulcular Debridement: The purpose of this step is to remove the residual debris while inducing blood coagulation. The laser tip is gently brushed through the entire periodontal pocket in a sweeping motion from the base to the top of the pocket. Setting: RFPT5, 1.5W, 10% air, 10% water, 30 Hz, H mode (iPlus preset).
- 8) Compress: The surgical site is compressed with moistened 2 x 2 gauze using finger pressure for five minutes to achieve hemostasis.
- ~~9) *Optional -Biostimulation: Application of the 940nm diode laser with pain therapy handpiece. Setting: 3.0W for 30 seconds directed toward the apices and another 30 seconds directed toward the gingival margins. THIS OPTIONAL STEP WILL NOT BE INCLUDED IN THIS STUDY— CONSIDER FOR FUTURE STUDIES.*~~

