**Abstract**

Laser use in dentistry has grown rapidly in recent years. This is especially true for the use of lasers in periodontics. Laser therapy is thought to provide marked improvement in non-surgical treatment outcomes resulting in a reduction in the need for surgery when compared to conventional periodontal therapy (scaling and root planing) alone. The research supporting these claims is limited to a few short-term studies and case reports. Questions remain regarding the long-term benefits of adjunctive laser therapy in the treatment of chronic periodontitis. However, if laser therapy proves to be advantageous, it has the potential to have a significant impact on the treatment of chronic periodontitis. Periodontal health and stability must be demonstrated over time to substantiate the claim of achieving successful periodontal therapy with a reduced need for surgery. The aim of this randomized, controlled clinical study is to examine the clinical efficacy of laser therapy as an adjunct to scaling and root planing in comparison to conventional non-surgical periodontal therapy alone. Clinical parameters including plaque index, gingival index, bleeding on probing, periodontal probing depth and clinical attachment levels will be measured at baseline and at 1, 3, 6, 9, and 12 months following treatment. Intraoral digital periapical radiographs and cone beam computed tomography scans will be taken at baseline, 6 and 12 months to evaluate changes in periodontal bone levels. This non-invasive method of evaluating changes in periodontal bone levels will serve as a surrogate indicator of periodontal bone regeneration.

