To date, only two human clinical studies have attempted to evaluate the potential of laser therapy on periodontal regeneration. Specifically, these two studies tested LANAP® (Laser Assisted New-Attachment Procedure), using an FDA approved laser (PerioLase, Millennium Dental Technologies, Inc.) and patented protocol marketed for the treatment of chronic periodontitis. In 2007, Yukna et. al., published human histological results of a small clinical study using the LANAP protocol. Six pairs of single rooted teeth with subgingival calculus in six patients (three men and three women) were scaled and root planed with ultrasonic and hand scalers. One tooth of each pair was also treated with the LANAP® protocol. Three months after treatment, all treated teeth were removed en bloc for histologic processing. The authors reported periodontal regeneration with new cementum and new connective tissue attachment in all six of the LANAP® treated specimens, whereas five of the six control specimens had a long junctional epithelium with no evidence of new attachment or regeneration. In 2012, Nevins, et. al., published histological findings of 10 teeth removed en bloc nine months after treatment with the LANAP® protocol. They reported that five teeth showed evidence of some periodontal regeneration with new cementum, periodontal ligament and alveolar bone. One tooth showed evidence of new attachment with new cementum and inserting collagen fibers, and four teeth showed healing via long junctional epithelium. Critically, there were no controls in this study. Subsequently in 2014, Nevins, et. al., published the nine month clinical findings of the above study. There were eight patients with a total of 930 sites treated with full-mouth LANAP® at a single clinical center. Briefly, the authors reported a mean probing depth reduction from  $4.62 \pm 2.29$  mm to  $3.14 \pm 1.48$  mm after nine months ( $p < 0.05$ ). Recession increased from  $0.86 \pm 1.31$  mm to  $1.52 \pm 1.62$  mm. Analysis revealed that 73% of all sites decreased probing depth, 21% of sites had no change and 6% of sites increased probing depth; 58% of

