**CONFIDENTIAL**

---

sites gained attachment, 24% of sites showed no change in attachment and 18% of sites lost clinical attachment. Again, there were only eight patients in the study and there were no controls.

Clearly, well-designed, controlled clinical trials are needed to evaluate the effectiveness of lasers as an adjunctive therapy in the non-surgical treatment of chronic periodontitis.

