**Specific Aims**

The purpose of this study is to evaluate whether adjunctive laser therapy will yield more favorable clinical results than conventional therapy alone in the treatment of chronic periodontitis. The laser to be evaluated in this study is the Waterlase iPlus (Er,Cr:YSGG) laser.

The specific aims of this research are to:

1. Evaluate the effect of adjunctive laser (Er,Cr:YSGG) therapy on periodontal disease resolution using clinical parameters to assess improvement in periodontal health.
2. Evaluate the effect of adjunctive laser (Er,Cr:YSGG) therapy on periodontal regeneration using radiographic imaging to assess changes bone levels (as a surrogate marker of regeneration).

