**CONFIDENTIAL**

---

**Protocol Summary.** Following a thorough review of the patient's health history, clinical and radiographic examination, qualified subjects will sign an informed consent to be enrolled in the study. Treatment will be randomly assigned to quadrants and implemented according to the following standardized protocol:

1. Participants will be provided with oral hygiene aids and receive standardized oral hygiene instructions.
2. One week following oral hygiene instruction participants will return for collection of baseline clinical data including:
  - a. Plaque index
  - b. Gingival index
  - c. Bleeding on probing
  - d. Probing pocket depth
  - e. Gingival recession
  - f. Clinical attachment levels (calculated)
3. Each qualifying quadrant will be randomly assigned to scaling and root planing alone or scaling and root planing with adjunctive laser treatment.
4. At the time of treatment, occlusal contacts will be evaluated and appropriate occlusal adjustments will be made if deemed necessary (i.e. adjustment of occlusal interferences and/or fremitus).
5. Each quadrant will be treated, according to assigned group, at separate visits that are at least two weeks apart.
6. A plaque sample (biofilm) will be collected from selected sites in each qualifying quadrant prior to treatment for microbial analysis. This will be repeated at the re-evaluation appointments.
7. A visual analog scale will be used to assess pain during the first 24-48 hours.
8. Subjects will keep a log of the type and amount of analgesics taken.
9. Subjects will be evaluated at 3, 6, 9 and 12 months after therapy.
10. Periodontal recall maintenance will be provided, as needed, at 3, 6, 9 and 12 months. Oral hygiene instructions will be reinforced at each visit.

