**CONFIDENTIAL**

- 
11. Radiographic imaging (intraoral digital periapical radiograph and cone beam computed tomography scan) will be taken of each quadrant/treatment site at baseline, 6 and 12 months.
  12. Subjects will complete a written survey to answer questions about their satisfaction with the treatment provided.

**Treatment Groups.** Each subject must have at least two qualifying quadrants. One quadrant will be randomly assigned to one of the two treatment groups (control or test) and the second quadrant will be assigned to the other group. Every subject will have at least one quadrant assigned to the control group and one quadrant assigned to the test group and will thus serve as their own control. Each additional qualifying quadrant in the same individual will be assigned to the next treatment group (i.e. if the second quadrant was assigned to the test group, then the third quadrant will be assigned to the control group and the fourth quadrant will be assigned to the test group). Treatment of multiple quadrants in the same group for the same subject will be treated on the same visit in order to maintain a reasonable follow-up / data collection schedule. All treatment will be completed with local anesthesia.

Group 1 (control):

- Non-surgical, mechanical scaling and root planing with hand instruments and ultrasonic device.

Group 2 (test):

- Non-surgical, mechanical scaling and root planing with hand instruments and ultrasonic device including the use of adjunctive WaterLase iPlus (Er,Cr:YSGG) laser therapy according to the following REPAIR protocol. See Attachment 1.

**Post-treatment Instructions.** All patients will be provided with specific oral hygiene instructions. From day two until day seven, patients will be instructed to brush with a

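### Does gingivectomy in the laser arm alone oblige the plan to rank attachment level above probing depth?

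*Combined protocol and SAP*

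**What the plan says.** Under Treatment Groups, the control quadrants receive "Non-surgical, mechanical scaling and root planing with hand instruments and ultrasonic device". The test quadrants receive the same, "including the use of adjunctive WaterLase iPlus (Er,Cr:YSGG) laser therapy according to the following REPAIR protocol". That regimen is Attachment 1, and its step 2 is: "The outer pocket gingival epithelium is removed (and gingivectomy performed if pseudopocket) with laser". Gingivectomy is thus conditional on a pseudopocket and occurs in the test arm only.

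Baseline precedes treatment. Under Protocol Summary, item 2, one week after hygiene instruction "participants will return for collection of baseline clinical data including" the indices, probing depth, recession and calculated attachment level.

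Aim 1 (Specific Aims) concerns the effect of the laser "on periodontal disease resolution using clinical parameters to assess improvement in periodontal health". The Abstract lists the measures side by side: "Clinical parameters including plaque index, gingival index, bleeding on probing, periodontal probing depth and clinical attachment levels will be measured". Clinical Measurements lists eight items, unranked. Probing depth (PD), recession and clinical attachment level (CAL) are all taken at six sites per tooth in both arms. CAL is marked as calculated, without a formula. Data Analysis defers to a biostatistician. Protocol Summary, item 11, adds periapical and cone beam imaging of each treated site at baseline, 6 and 12 months.

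**The concern.** PD is the distance from the gingival margin to the base of the pocket. Cutting the margin away shortens that distance even if the base has not moved. Because only one arm can have margin excised after baseline, a test-minus-control PD difference is a valid effect of the whole regimen on PD, but it mixes tissue removal with healing. If it were reported alone as disease resolution, Aim 1 would be answered too favourably.

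Two features sharpen the worry. No outcome or time point is placed first in the text available, so PD could become the headline once the data are in. And CAL separates the two components only if recession carries a sign where the margin lies coronal to the reference point, which the plan does not spell out.

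**Working it through.** The plan gives no effect size, SD, alpha or power, so there is no figure of its own to reproduce. Three checks were made.

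**1. Can PD and attachment diverge in the plan's own background?** Inputs are the nine-month uncontrolled LANAP series (Background and Significance, Regeneration vs. Repair).
- PD reduction: 4.62 − 3.14 = 1.48 mm.
- Recession increase: 1.52 − 0.86 = 0.66 mm.
- Implied attachment gain: 1.48 − 0.66 = 0.82 mm.
- Share of PD reduction due to margin movement: 0.66 / 1.48 = 45%.

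By site, "Analysis revealed that 73% of all sites decreased probing depth", while 58% of "sites gained attachment, 24% of sites showed no change in attachment and 18% of sites lost clinical attachment". So they can diverge. But the 0.82 mm and 45% assume signed recession averaged over the same sites, which the protocol does not report for that series. It also used another laser, had no controls, and no cause is given for the recession. It illustrates the point and does not estimate an effect for this trial.

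**2. How large could the PD effect be here?** Assumptions: paired t-test, n = 35 (Materials and Methods), two-sided alpha 0.05, SD of the within-patient difference 0.6 to 1.0 mm, no true healing difference.

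Net shift = share of sites × (mm excised and not regrown − extra shrinkage at matching control sites).

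Chance of significance = P(|T| > t(0.975, 34)), where T is noncentral t with 34 df and noncentrality (shift / SD) × √35.

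| Scenario (2 mm excised) | Net shift | SD 0.6 | SD 0.8 | SD 1.0 |
|---|---|---|---|---|
| 1% of sites, no regrowth, no extra control shrinkage | 0.01 × 2 = 0.02 mm | 5.4% | 5.2% | 5.2% |
| 10%, half regrows and controls shrink 1 mm more | 0.10 × (1 − 1) = 0 | 5.0% | 5.0% | 5.0% |
| 10%, only one of these happens | 0.10 × 1 = 0.10 mm | 16.0% | 11.1% | 8.9% |
| 10%, neither happens | 0.10 × 2 = 0.20 mm | 48.3% | 30.1% | 21.0% |

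Higher shares push further. With 20% of sites, 2 mm, no offset and SD 0.75 mm, the shift is 0.40 mm and the chance 87%. With 30%, 2 mm and SD 0.5 mm it exceeds 99%. The share of sites, millimetres excised, regrowth, control shrinkage and SD are all assumed. These are chances of a real PD difference that might be misread, not type I error for PD.

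**3. Does the planned data set separate the two components?** Take PD 5 mm with the margin 2 mm coronal to the reference point, and 2 mm excised.
- Signed recession: CAL = 5 − 2 = 3 mm before and 3 + 0 = 3 mm after, a gain of 0.
- Recession set to zero when the margin is coronal: CAL = 5 + 0 = 5 mm before and 3 mm after, an apparent gain of 2 mm.

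Computed with its sign, CAL removes the artefact completely. Only the zero-floor version fails, and nothing in the documents says that version will be used.

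**The case for a change.** The strongest case for acting is this. With no outcome ranked and analysis deferred, nothing prevents PD being chosen after the data are seen. Naming PD as primary would close the general gap and leave this one open. The sign rule has to be settled before baseline, because readings recorded without a sign cannot be recovered. Sites qualify on PD of 5 mm or more with no site-level attachment threshold, and the regimen itself provides for gingivectomy without saying how often. The remedy would cost a few sentences and no new measurement.

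Part of that stands: the arms differ in this step, CAL has no stated formula, and no primary outcome is named. The last is a general matter. PD is not ranked above anything either, and gingivectomy is only one consideration in choosing.

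The rest does not carry. Aim 1 speaks of clinical parameters in the plural, and no section says PD alone will show resolution. PD, recession and CAL come from the same sites, so anyone reporting PD has the other two to hand. Bone imaging gives evidence that gingivectomy cannot move, although step 6 of Attachment 1 acts on bone directly, so this independence is from margin excision only. Entry requires chronic periodontitis with an interproximal intrabony defect in each quadrant, so pseudopockets may be few.

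Putting CAL first also has a price. With 35 pairs, 80% power needs a true difference of 0.29 to 0.49 mm at SD 0.6 to 1.0 mm. If combining two readings made CAL's SD 20% larger (assumed), that becomes 0.35 to 0.59 mm. At the unchanged difference, power falls to 65%, or 50 patients are needed instead of 35. The Hypothesis covers clinical and radiographic results and the need for surgery, and does not make attachment gain the governing outcome.

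**Conclusion.** No change to the plan follows. The asymmetry is real, but a PD difference remains a valid effect of the regimen on PD. Followed as written, the plan yields the measurements that show how much of the difference is margin and how much is attachment. What is unstated is the CAL formula with its sign and the reading of PD beside recession and CAL. An analyst can fill that detail sensibly: attachment level is a distance from a fixed point to the pocket base, and only the signed sum returns it. A wrong result would need recession floored at zero, or PD reported alone as healing, and the documents propose neither. Whether PD or CAL comes first is a fair trade-off between ease of interpretation and precision.

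The size is unknown and possibly negligible. In the 1% and 10% scenarios the chance of a significant PD difference from margin removal alone runs from 5% to 48%, and it is higher if more sites are excised. All of this rests on assumed inputs. The judgement also depends on the text available, from which some pages were removed.
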